#### “2.4.3 List of occurrence status of adverse reactions (Important identified risk)”

Patients included in analysis: Patients included in safety analysis

Objective of analysis: In adverse reactions that occurred in the period subject to safety analysis, summary statistics of days to onset of important identified risks, the number of patients by the outcome, and days to outcome (Resolved or resolving) is shown.

Analysis items: The number of patients in whom adverse reactions occurred and rate of these patients to those included in analysis, the number of patients in whom serious adverse reactions occurred and rate of these patients to those included in analysis by types of important identified risks (important identified risk, PT) in the period subject to safety analysis should be calculated. In addition, summary of statistics of days to onset of adverse reactions (the number of patients, the mean, median, maximum values), the number of patients by outcome, summary of statistics of days from onset to outcome (Resolved or resolving) (the number of patients, the mean, median, minimum, and maximum values) by PT and important identified risks (total number of PT code) should be calculated.

Notes: If there are events with same PT in one patient, “2.4.1 List of occurrence status of primary items” should be referred to.

#### “2.5 List of occurrence status of adverse reactions by presence or absence of self-administration”

Patients included in analysis: Patients included in safety analysis

Objective of analysis: Occurrence status of adverse reactions by presence or absence of self-administration is shown.

Analysis items: Following items should be aggregated by presence or absence of self-administration in adverse reactions that occurred in the period included in safety analysis.

The number of patients included in the survey, the number of patients in whom adverse reaction occurred, the number of adverse reactions, the number of patients in whom

adverse reactions occurred and rate of these patients to those included in analysis by types of adverse reactions (SOC, PT) should be calculated.

#### “2.7 List of occurrence status of adverse reactions”

Patients included in analysis: Patients included in safety analysis

Objective of analysis: Occurrence status of adverse reactions by the time of onset is shown.

Analysis items: The number of patients should be calculated by the period for following items in patients in whom adverse reaction occurred in the period subject to safety analysis.

The number of patients included in survey, the number of patients in whom adverse reaction occurred, the number of adverse reactions (95% confidence interval), the number of patients in whom adverse reactions occurred and rate of these patients to those included in analysis by types of adverse reactions (SOC, PT) should be calculated.

Notes: The event that occurred first of all events with same PT in one patient should be included in analysis. Aggregation of data including the time of onset for the first-onset adverse reaction in Time Allowance defined in “12.2 Time of evaluation of adverse reactions”. When the number of patients for events included in analysis is counted, data should be made invalid according to patient number and time of onset, and when the number of SOC is counted, data should be made invalid according to patient number, time of onset, and SOC for aggregation.

The number of patients included should be counted according to following definitions except for patients who discontinued the survey (patients who used this drug within the follow-up period) so that patients included in evaluation corresponding to Time Allowance defined in “12.2 Time of evaluation of occurrence status of adverse reactions” can be included. For patients who discontinued the survey, the patients included in the period until the time when 28 days has passed from the last date of the final administration of this drug should be counted.

- Patients who were followed up for 52 weeks:

Patients who received this drug “for 52 weeks or longer and shorter than 104 weeks after the administration start” should be included.

- The number of patients who were followed up for 104 weeks:

Patients who received this drug “for 104 weeks or longer and shorter than 156 weeks after the administration start” should be included.

- The number of patients who were followed up for 156 weeks:

Patients who received this drug for longer than 156 weeks after the administration start should be included.

The number of patients in whom adverse reactions occurred should be counted by the period during which at least one adverse reaction is noted.

Incidence should be calculated by the time of evaluation to calculate Clopper-Pearson confidence interval.

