## 2. ■ 2. Definition of terms and abbreviations

Terms and abbreviations used in this analysis plan are defined as follows:

Terms and abbreviations	Definition
Patients who were followed up for 52 weeks (patients collected for the first volume)	Patients who started to receive this drug between August 16, 2014 and August 15, 2015.
Patients included at the 104th week of follow-up (patients collected for the first and second volume)	Patients who started to receive this drug between August 16, 2013 and August 15, 2014.
Patients included at the 156th week of follow-up (patients collected for the first, second, and third volume)	Patients who started to receive this drug by August 15, 2013.
Adverse events	Any unfavorable and unintended sign (including an abnormal laboratory finding), symptom, or disease, regardless of whether they are related to this drug or not
Adverse events that occurred during the period subject to safety analysis	
Adverse events that occurred from the start date of administration until the time as follows should be included.
 
 
Patients included at the 52th week of follow-up: The start date of administration of this drug + 392 days (56 weeks)
 
Patients included at the 104th week of follow-up: The start date of administration of this drug + 756 days (108 weeks)
 
Patients included at the 156th week of follow-up: The start date of administration of this drug + 1120 days (160 weeks)
 
Patients who discontinued to receive this drug: The last date of administration of this drug + 28 days
 

Adverse events that occurred in a period except for the period subject to safety analysis	
Adverse events that occurred before the start date of administration or after the following timing should be included
 
 
Patients included at the 52th week of follow-up: The start date of administration of this drug + 392 days (56 weeks)
 
Patients included at the 104th week of follow-up: The start date of administration of this drug + 756 days (108 weeks)
 
Patients included at the 156th week of follow-up: The start date of administration of this drug + 1120 days (160 weeks)
 
Patients who discontinued to receive this drug: The last date of administration of this drug + 28 days
 

Adverse reaction	Among adverse events, those for which causal relationship with this drug cannot be ruled out should be included

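### Table 2.7 counts patients observed for 29 of 364 days as whole patients, so late adverse-reaction incidence is too low by about 0.92 times their share of the denominator

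*SAP*

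**What the plan says.** Section 2 forms three cohorts by start date: a 52-week cohort (starts August 16, 2014 to August 15, 2015), a 104-week cohort (August 16, 2013 to August 15, 2014) and a 156-week cohort (starts up to August 15, 2013). Their safety periods end at start + 392, + 756 and + 1120 days, or at last dose + 28 days for patients who discontinued.

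Section 12.2 takes the start date as day 1 and sets the two late onset windows at days 365-728 and 729-1092.

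The notes to Table 2.7 in section 13.2 define the denominators. "The number of patients included should be counted according to following definitions except for patients who discontinued the survey". Continuing patients of the 52-week cohort go with those treated "for 52 weeks or longer and shorter than 104 weeks after the administration start", and those of the 104-week cohort with those treated "for 104 weeks or longer and shorter than 156 weeks after the administration start". Discontinued patients are handled separately: "For patients who discontinued the survey, the patients included in the period until the time when 28 days has passed" since the last administration are counted.

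Only reactions inside the safety period enter the numerator. For repeated events, "The event that occurred first of all events with same PT in one patient should be included in analysis". At patient level, "The number of patients in whom adverse reactions occurred should be counted by the period during which at least one adverse reaction is noted". Finally, "Incidence should be calculated by the time of evaluation to calculate Clopper-Pearson confidence interval". No person-time rate or exposure weighting is specified.

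**The concern.** A continuing patient of the 52-week cohort enters weeks 52-104 at the moment follow-up is about to close. Section 10.1 caps the last treatment date at start + 364 days, which is day 365, the first day of the window. Only the 28-day safety tail remains. The same happens to the 104-week cohort in weeks 104-156. These patients add a full unit to the denominator but almost no opportunity to add to the numerator.

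The effect runs one way: late incidence looks low, and a constant risk looks like one that falls with longer use. Its size depends on how many patients started in which year, not on the drug.

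Table 2.7 is the only table of incidence by time since start, and the only table in Chapter 13 that asks for a confidence interval. Section 3.1 says the results feed regulatory reporting and the reassessment application. The primary survey items in section 4.1 include tuberculosis and malignant tumour, for which late onset is of interest.

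**Working it through.** The SAP states no incidence figure to reproduce. Its own week-to-day conversions are correct: 56 × 7 = 392 and 108 × 7 = 756.

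**Inputs.** Windows from section 12.2; ends of the safety period from section 2; cap on last treatment date from section 10.1. The share *s* of short-observed patients in each denominator is not given (section 4.3 leaves the number of patients undecided), so it is varied.

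**Step 1: observed days.** With start as day 1, start + 392 is day 393 and start + 756 is day 757.
- Weeks 52-104: 393 − 365 + 1 = 29 of 364 days.
- Weeks 104-156: 757 − 729 + 1 = 29 of 364 days.
- 29/364 = 0.080, so 0.920 of the window is unobserved. Reading the limits as days 392 and 756 gives 28 days and 0.923.

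**Step 2: understatement.** With constant hazard h, the risk over d days is r(d) = 1 − exp(−h·d). The table shows (1 − s)·r(364) + s·r(29), so the relative understatement is s × (1 − r(29)/r(364)). The bracket is 0.920 at a window risk of 1%, 0.916 at 10%, 0.912 at 20% and 0.893 at 50%.

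For an assumed true window risk of 20%:

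| Share s | Table shows | Understatement |
|---|---|---|
| 0.1 | 18.2% | 9.1% |
| 0.3 | 14.5% | 27.4% |
| 0.5 | 10.9% | 45.6% |
| 0.7 | 7.2% | 63.8% |

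The interval gives no protection. With 100 patients counted and s = 0.5, the expected 11 patients with a reaction give a Clopper-Pearson interval of 5.6% to 18.8%, which excludes the true 20%.

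**Step 3: patients who stop mid-window.** They are also counted whole. At s = 0.5 and 20% risk, a further 10% of patients observed for half the window raises the understatement from 45.6% to 50.3%.

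**Step 4: one illustration of s.** Assume even accrual, with the 156-week cohort starting on May 16, 2013 (section 2 gives no lower limit). That gives 365, 365 and 92 start days.
- Weeks 52-104: s = 365/822 = 44.4%; 0.916 × 0.444 = 41% understatement.
- Weeks 104-156: s = 365/457 = 79.9%; 0.916 × 0.799 = 73%.

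**Step 5: simulation.** One reaction type, assumed at 10 per 100 patient-years, with 15% of patients per year stopping treatment. Approximate percentages from Table 2.7 as written:

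| Cohort mix | Weeks 52-104 | Weeks 104-156 |
|---|---|---|
| Even accrual | 4.7% | 2.0% |
| Equal cohorts | 5.5% | 3.9% |
| 80% in 156-week cohort (1:1:8) | 7.2% | 6.5% |
| All in 156-week cohort | 8.0% | 7.2% |

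The true hazard is the same in every row.

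**Step 6: does a rate repair it?** In the same simulation:
- First onsets over all observed patient-years give 8.6 and 7.8-7.9 per 100, too low by about 14% and 21%. Patients who have already had the reaction keep adding time but cannot count again.
- With time at risk cut at first onset, the rate is 9.99-10.04 per 100 in both windows for every mix (truth 10).
- The percentage restricted to cohorts scheduled for the whole window is 7.9-8.0% and 7.2% in every mix.
- For an any-reaction row (10 reaction types at 2 per 100 patient-years each), the table as written shows 9.9% and 4.5% under even accrual, against 16.4% and 16.1% if all were in the 156-week cohort. The rate, with time cut at the first counted reaction in the window, is 19.6-19.7 and 19.1-19.4 per 100 in every mix.

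**The case against.** **The denominator wording is unclear.** Read literally, it places each cohort in one window only. A continuing patient whose last dose fell between start + 350 and start + 363 days (continuing under section 10.1) might also fail the 52-week condition. This stands as a drafting ambiguity. The one-window reading makes matters worse, because every continuing patient in each late window would then be a short-observed one. Leaving out the second group would lower the share, by an amount the SAP does not allow one to work out.

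**The table may not aim at a full 52-week risk.** Its stated aim is occurrence by time of onset, and the windows differ in length, so the percentages are not comparable rates anyway. The unequal windows are a fair point. But a percentage labelled incidence for weeks 52-104, with an exact binomial interval, will be read as the risk in that window, and here it also changes with the cohort mix.

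**The size is unknown.** This stands. Patients carried over from the clinical trial would enlarge the 156-week cohort and shrink the affected share. The 41% and 73% figures are illustrations only.

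**Other outputs help.** Table 1.1.1 [2] gives cohort counts, Tables 2.4.1-2.4.3 give days to onset, and the patient list in section 13.1 gives individual dates. Overall incidence and the tests in Table 2.9 do not use these denominators. All true, but correcting Table 2.7 from these outputs means redoing it.

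**The remedy is heavy for one descriptive table.** It needs two definitions of time at risk. The any-reaction rate also drifts slightly below the input of 20 per 100, though it is stable across mixes. The restricted percentage rests on fewer patients: under even accrual it drops about 80% of the weeks 104-156 denominator and keeps only the earliest starters. These costs are real and should be stated with the results.

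**Conclusion.** The concern holds. By the SAP's own day counts, continuing patients of the 52- and 104-week cohorts can contribute a reaction on 29 of 364 days but count as whole patients. Incidence in weeks 52-104 and 104-156 is too low by about 0.92 times their share of the denominator, and patients who stop mid-window add to this.

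The 29 days follow from the document alone. The 0.92 factor also needs a roughly constant hazard and falls to about 0.89 when the window risk is 50%. The absolute size cannot be fixed, because the SAP gives no cohort sizes: the possible range is 0% to 92%. The direction is not in doubt. Since the table is descriptive and no test depends on it, this should be corrected but does not threaten the plan's other results.

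**What to change.** In Table 2.7, report first-onset reactions per 100 patient-years at risk in each window, with exact Poisson 95% intervals. Time at risk in a window ends at the earliest of:

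- first onset of the reaction being counted;
- end of the safety period (start + 392, 756 or 1120 days, or last dose + 28 days for patients who discontinued);
- end of the window.

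For preferred-term rows, first onset means the first ever of that term, so a patient with an earlier onset adds no later time. For system-organ-class and any-reaction rows, it means the first reaction counted in that row within the window, because the plan lets a patient count again in a later window.

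As a supplement, keep a percentage but restrict numerator and denominator to the 104- and 156-week cohorts for weeks 52-104, and to the 156-week cohort for weeks 104-156. List reactions on days 365-393 and 729-757 of the shorter cohorts separately so that none is lost. Reword the denominator note so that the windows each cohort enters are unambiguous.

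The cost is modest programming from dates the SAP already derives. A patient-year rate is less familiar than a percentage, which is why the restricted percentage stays beside it. That percentage no longer depends on the cohort mix, but it rests on fewer and earlier-starting patients and still counts mid-window stoppers in full. A footnote should say so.

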**“2.9 Incidence of adverse reactions (serious adverse reaction and adverse reaction) by patient characteristics”**

Patients included in analysis: Patients included in safety analysis

Objective of analysis: Incidence of adverse reactions should be shown by patient characteristics and factor analysis should be conducted.

Analysis items: In patients in whom adverse reactions occurred in the period subject to safety analysis, the number of all the patients, the number of patients with serious adverse reactions, and rate of these patients to those included in analysis, the number of the patients with adverse reactions and rate of these patients to those included in analysis, and test provided for the adverse reactions (Fisher’s exact test for nominal scale factors, and Mann-Whitney u test for ordinal scale factors) should be calculated by following patient characteristics:

Notes: Patient characteristics are as follows: Age (years), sex, disease duration (years), complication, hepatic function disorder as complication, renal impairment as complication, medical history, allergy history, smoking habit, self-administration as administration status of this drug, previously used drug/previous treatment, biological preparation adalimumab as previously used drug, biological preparation infliximab as previously used drug, steroid as previously used drug, immunomodulative drug as previously used drug, immunosuppressive drug as previously used drug, oral adrenocortical steroid as concomitant drug, oral mucosa recurrent aphthous ulcer as main symptoms of Behcet disease other than gastrointestinal symptoms, cutaneous symptoms as main symptoms of Behcet disease other than gastrointestinal symptoms, eye symptoms as main symptoms of Behcet disease other than gastrointestinal symptoms, ulcer of vulva as main symptoms of Behcet disease other than gastrointestinal symptoms, arthritis without deformity or rigidity as accessory symptoms of Behcet disease other than gastrointestinal symptoms, epididymitis as accessory symptoms of Behcet disease other than gastrointestinal symptoms, vascular lesion as accessory symptoms of Behcet disease other than gastrointestinal symptoms, moderate or higher degree central nervous lesion as accessory symptoms of Behcet disease other than gastrointestinal symptoms, diagnostic classification of Behcet disease, days until the last date of the administration, and mean daily dose.

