##### 2) Items related to safety

- [1] List of occurrence status of adverse reactions and infections
- [2] Factors that may contribute to safety
  - Incidence of adverse reactions by patient characteristics (sex, disease duration, smoking habit, presence or absence of complications, presence or absence of medical history, presence or absence of allergy, presence or absence of previous treatment, and presence or absence of concomitant drugs)
  - According to symptoms of Behcet disease other than gastrointestinal tract symptoms
  - According to changes in steroid dose in patients who receive steroid
- [3] Adverse events that occurred during or after administration of this drug

- List of occurrence status of serious adverse events

[4] Occurrence status of Self-administration error

[5] Contribution to safety when anti-adalimumab antibody is detected

3) Items related to efficacy

[1] Comprehensive evaluation of gastrointestinal symptoms, evaluation of gastrointestinal symptoms Behcet disease, evaluation of main symptoms of Behcet disease, evaluation of accessory symptoms, level of improvement in endoscopy findings, and CRP

[2] Factors considered to contribute to efficacy

- Efficacy by patient characteristics (sex, disease duration, smoking habit, presence or absence of complications, presence or absence of medical history, presence or absence of allergy, presence or absence of previous treatment, and presence or absence of concomitant drugs)
- According to symptoms of gastro-intestinal Behcet disease
- According to changes in steroid dose in patients who receive steroid
- Contribution to efficacy when anti-adalimumab antibody is detected

4) Items concerning patients with specific characteristics

List of occurrence status of adverse reactions/infections in patients with specific characteristics including children, the elderly, expectant and nursing mothers, patients with renal impairment, or patients with hepatic function disorder

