Chest X-ray and CT scanning	Either of “Chest X-ray” or “CT scanning” is implemented (if there is no check mark in box for implementation although test results are described, tests are deemed to have been implemented”). Tests were not implemented: Other than above situations
Drug previously used	Of data in which there are any descriptions about “previously used drug/previous treatment for gastro-intestinal Behcet disease”, data excluding that about previous treatment method is deemed to be previously used drug. Patients with description about previously used drug is deemed to have drug previously used. If there is no description in “previously used drug/previous treatment method for gastro-intestinal Behcet disease” and whether patients have drug previously used cannot be assessed, where there is drug previously used is deemed to be unknown/not described, and in any other situations, patients are deemed to have no drug previously used.
Presence or absence of use of previously used drug (aminosalicylic acid preparation)”	Based on “161206 drug list_addtion (Fix)CRO”, if there is a data on previously used drug corresponding to relevant drug code or there is a check mark in a box for aminosalicylic acid preparation in the survey sheet, patients are deemed to have previously received aminosalicylic acid preparation and in any other situations, patients are deemed not to have received aminosalicylic acid preparation.

Name of data	Derivation and calculation method
Presence or absence of previously used drug (steroid)	Based on “161206 drug list_addtion (Fix)CRO”, if there is a data on previously used drug corresponding to relevant drug code or there is a check mark in a box for steroid in the survey sheet, patients are deemed to have previously received steroid and in any other situations, patients are deemed not to have received steroid.
Presence or absence of previously used drug (immunomodulative drug)	Based on “161206 drug list_addtion (Fix)CRO”, if there is a data on previously used drug corresponding to relevant drug code or there is a check mark in a box for immunomodulative drug in the survey sheet, patients are deemed to have previously received immunomodulative drug and in any other situations, patients are deemed not to have received immunomodulative drug.

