Presence or absence of drug used for previously used drug (antibiotic)	Based on “161206 drug list_addtion (Fix)CRO”, if there is a data on previously used drug corresponding to relevant drug code or there is a check mark in a box for antibiotic in the survey sheet, patients are deemed to have previously received antibiotic and in any other situations, patients are deemed not to receive antibiotic.
Presence or absence of previously used drug (other drug)	Based on “161206 drug list_addtion (Fix)CRO”, if there is a data on “Other drugs than biological preparations” in the survey sheet and any data on previously used drug except for aminosalicylic acid preparation, steroid, immunomodulative drug, or antibiotic, patients are deemed to have previously received other drugs and in any other situations, patients are deemed not to have received other drugs.
Presence or absence of drug used for previously used drug (adalimumab)	Based on “161206 drug list_addtion (Fix)CRO”, if there is a data on previously used drug corresponding to relevant drug code, patients are deemed to have previously received adalimumab and in any other situations, patients are deemed not to have received adalimumab.
Presence or absence of previously used drug (infliximab)	Based on “161206 drug list_addtion (Fix)CRO”, if there is a data on previously used drug corresponding to relevant drug code, patients are deemed to receive infliximab and in any other situations, patients are deemed not to have previously received infliximab.
Presence or absence of previously used drug (other biological preparations)	Based on “161206 drug list_addtion (Fix)CRO”, if there is a data on “Biological preparations” in the survey sheet and any data on previously used drug except for adalimumab or infliximab, patients are deemed to have previously received other biological preparations and in any other situations, patients are deemed not to have previously received other biological preparations.

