Presence or absence of	Based on “161206 drug list addition (Fix)CRO”, if there is a data

Name of data	Derivation and calculation method
use of concomitant drug (aminosalicylic acid preparation)	on concomitant drug corresponding to relevant drug code, patients are deemed to concomitantly received aminosalicylic acid preparation and in any other situations, patients are deemed not to concomitantly receive aminosalicylic acid preparation.
Presence or absence of use of concomitant drug (steroid)	Based on “161206 drug list_addition (Fix)CRO”, if there is a data on concomitant drug corresponding to relevant drug code, patients are deemed to concomitantly receive steroid and in any other situations, patients are deemed not to concomitantly receive steroid.
Presence or absence of concomitant drug (immunosuppressive drug)	Based on “161206 drug list_addition (Fix)CRO”, if there is a data on concomitant drug corresponding to relevant drug code, patients are deemed to concomitantly received immunosuppressive drug and in any other situations, patients are deemed not to concomitantly receive immunosuppressive drug.
Presence or absence of concomitant drug (immunomodulative drug)	Based on “161206 drug list_addition (Fix)CRO”, if there is a data on concomitant drug corresponding to relevant drug code, patients are deemed to concomitantly receive immunomodulative drug and in any other situations, patients are deemed not to concomitantly receive immunomodulative drug.
Presence or absence of concomitant drug (enteral nutrient)	Based on “161206 drug list_addition (Fix)CRO”, if there is a data on concomitant drug corresponding to relevant drug code, patients are deemed to concomitantly received enteral nutrient and in any other situations, patients are deemed not to concomitantly receive enteral nutrient.
Presence or absence of concomitant drug (colchicine)	Based on “161206 drug list_addition (Fix)CRO”, if there is a data on concomitant drug corresponding to relevant drug code, patients are deemed to concomitantly received colchicine and in any other situations, patients are deemed not to concomitantly receive colchicine.
Presence or absence of concomitant drug (Others)	If there is data with descriptions about concomitant drug other than immunosuppressive drug, immunomodulative drug, enteral nutrient, and colchicine, patients are deemed to have use of other concomitant drug, and in any other situations, patients are deemed to have no concomitant drug.

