Detailed classifications of medical history	tuberculosis, bacterial bronchitis, nontuberculous mycobacterial infection, aplastic anaemia, pancytopenia, malignant tumour, others
Previously used drug/previous treatment	Absent, present, unknown, not described
Classification of biological preparation as previously used drug/previous treatment	Adalimumab, infliximab, others
Classification of drugs other than biological preparation as previously used drug/previous treatment	Biological preparation, aminosalicylic acid preparation, steroid, immunomodulative drug, antibiotic, other previously used drug, operation, other previous treatment
Concomitant drug	Absent, present, unknown, not described
Detailed classification of concomitant drugs	Aminosalicylic acid preparation, oral adrenocortical steroid, immunomodulative drug, immunosuppressive drug, enteral nutrient, colchicine, others
Combination therapy	Absent, present, unknown, not described
Detailed classification of combination therapy	Operation, others
Endoscopy	Absent, present, unknown, not described

data	Method of dividing hierarchy
Detailed classifications of endoscopy	Ileocecum, colon, esophagus, others
Level of improvement in endoscopy findings	Remission or scar, shrinkage, no change, aggravation, not assessed
Evaluation of gastrointestinal symptoms	
0,1,2,3,4
 
0: No symptom
 
1: There was symptom in last 2 weeks but daily living activities were rarely disturbed.
 
2: There was symptom in last 2 weeks and daily living activities were slightly disturbed.
 
3: There was symptom in last 2 weeks and daily living activities were disturbed.
 
4: There was symptom in last 2 weeks and daily living activities were severely disturbed.

Detailed classifications of gastrointestinal symptoms	Abdominal pain, diarrhoea, others (including bloating, abdominal tenderness, haemorrhage)
Self-administration	Absent, present
Self-administration error	Absent, present, unknown, not described
Drug used after the discontinuation of this drug	Absent, present, unknown, not described
Detailed classifications of drug used after the discontinuation of this drug	Aminosalicylic acid preparation, steroid, immunomodulative drug, biological preparation, other drug
Level of overall improvement	Significant improvement, improvement, ineffective
Detailed classifications of level of overall improvement for patients with improvement or higher level of improvement	Significant improvement, improvement

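### Tables 2.9 and 3.4 omit the any-concomitant-drug factor that SAP Section 5.1 names, and both list a prior-immunosuppressive factor that the SAP never defines

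*SAP*

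**What the plan says.** Section 5.1 lists the characteristics by which the incidence of adverse reactions will be examined. The list ends with "presence or absence of previous treatment, and presence or absence of concomitant drugs", and the efficacy items in the same section name the same characteristics.

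The tests themselves are in Table 2.9 (Section 13.2) and Table 3.4 (Section 13.3), which carry the same factor list. The part on drug exposure ends with "immunosuppressive drug as previously used drug, oral adrenocortical steroid as concomitant drug". No other concomitant-drug factor appears in either list.

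Section 10.1 defines the variables. For previous drugs, its residual class takes "any data on previously used drug except for aminosalicylic acid preparation, steroid, immunomodulative drug, or antibiotic". For concomitant drugs it derives an overall present/absent variable and a set of classes. One of these covers immunosuppressive agents, where on a drug-code match "patients are deemed to concomitantly received immunosuppressive drug".

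Section 11 gives the matching categories. Previous drugs other than biologics are grouped under "Biological preparation, aminosalicylic acid preparation, steroid, immunomodulative drug, antibiotic, other previously used drug, operation, other previous treatment". Concomitant drugs are grouped under "Aminosalicylic acid preparation, oral adrenocortical steroid, immunomodulative drug, immunosuppressive drug, enteral nutrient, colchicine, others".

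**The concern.** The two factor tables are where the survey meets its third objective in Section 4.1, finding factors that may contribute to safety and efficacy. If their rows do not match the definitions in Sections 5.1, 10.1 and 11, two things go wrong. A comparison that the plan commits to is never produced, and a programmer has to invent a rule for a row that the plan does not define.

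The gap also carries forward. The second table headed 2.9, which splits reactions by seriousness, SOC and PT, is produced only for characteristics that were significant in the first. A factor without a row gets no test and therefore no breakdown.

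**Working it through.** No figure in the plan is at issue. The check sets the factor lists beside the definitions.

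**Step 1: Section 5.1 against Tables 2.9 and 3.4.** Section 5.1 names eight characteristics: sex, disease duration, smoking, complications, medical history, allergy, previous treatment and concomitant drugs. Seven of the eight have a row in both tables, with previous treatment entering as the combined previous drug/previous treatment variable. The eighth, concomitant drugs, has none: 8 − 7 = 1 missing, in each table.

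**Step 2: drug-exposure rows against their definitions.** Each table lists 28 factors. Six concern previous drugs or treatment and one concerns concomitant drugs.

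| Exposure | Derived in 10.1 | Category in Section 11 | Row in 2.9 and 3.4 |
|---|---|---|---|
| Previous drug/treatment, any | yes | yes | yes |
| Previous adalimumab | yes | yes | yes |
| Previous infliximab | yes | yes | yes |
| Previous steroid | yes | yes | yes |
| Previous immunomodulative | yes | yes | yes |
| Previous immunosuppressive | **no** | **no** | **yes** |
| Concomitant drug, any | yes | yes | **no** |
| Concomitant steroid | yes | yes (oral) | yes (oral) |
| Concomitant immunosuppressive | yes | yes | **no** |

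One of the 28 factors therefore has no definition. It cannot be another name for the previous immunomodulative row, because both stand as separate factors in the same list.

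**Step 3: whether another table supplies the comparison.** In Section 13.2, the remaining tables that split reactions by a patient characteristic do so by self-administration (2.5), hepatic function disorder (2.13.1), central nervous lesion (2.13.5), renal impairment (2.14.1) and age group (2.16.1). None uses a concomitant drug. In Section 13.3 only Table 3.4 compares efficacy by patient characteristics. Concomitant classes are otherwise tabulated as a distribution in Table 1.12.1.

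**The case against.** Several points against this carry weight.

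- **Steroid is tested.** A reader might infer that the effect of co-immunosuppression on adverse reactions goes unassessed. The documents do not support that, because concomitant oral steroid is a factor in both tables. The gap concerns any concomitant drug and the concomitant immunosuppressive class.
- **The missing definition is a missing row, not an impossibility.** Section 10.1 classifies previous and concomitant drugs from what appears to be the same coded drug list, and that list evidently carries immunosuppressive codes. Prior use could be derived once a rule is written.
- **Where prior immunosuppressives now fall is unknown.** It is tempting to say that they land in the residual other-drug class. That depends on the drug-code list and the survey-sheet boxes, neither of which is shown. Some agents may be coded as immunomodulative.
- **The intended meaning is open.** A reader might infer that the row is the concomitant class under the wrong heading, since that is the only immunosuppressive variable derived. But the row directly follows other previous-drug factors, so a forgotten derivation is just as plausible.
- **Some information is reported.** Listing 2.3 shows the main concomitant drug and the number of drugs beside each patient's reactions, and Listing 1.16 shows concomitant drugs for the antibody-detected patients it lists. These are listings, not comparisons.
- **The comparison would be weak.** Table 2.9 tests any adverse reaction, so it would not answer a question about infection or tuberculosis directly. The concomitant variable is ever/never during treatment and can include a drug started after the reaction.

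These points limit what can be claimed. They remove neither the mismatch with Section 5.1 nor the undefined row.

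**Conclusion.** The point stands in two parts. Tables 2.9 and 3.4 leave out a factor that Section 5.1 names for both safety and efficacy and that Section 10.1 derives. Both also list prior immunosuppressive use, which the SAP does not define, while concomitant immunosuppressive use is defined but compared nowhere.

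In each table this is one of eight named characteristics missing and one of 28 factors undefined. The effect on any rate or p value cannot be estimated, because the SAP gives no co-medication frequencies. Section 5.1 commits only to the presence or absence of concomitant drugs, so rows for the remaining concomitant classes, including immunomodulative drugs, are optional. The conclusion rests on the SAP text alone and assumes nothing about how the unseen drug list codes individual agents. It is a correction that should be made before the tables are programmed.

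**What to change.** In Tables 2.9 and 3.4:

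1. Add a row for any concomitant drug, as Section 5.1 requires.
2. Add a row for concomitant immunosuppressive drug, using the existing 10.1 derivation. The any-drug row would show little contrast if most patients take something, so the class row is worth having.
3. Reconcile the undefined row. If the concomitant class was meant, relabel it, and item 2 is then met. If prior use was meant, keep it, write its derivation in 10.1 and add a class in Section 11, separate from the immunomodulative and other-drug classes.

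One clause needs checking before the concomitant variable is used. As worded, 10.1 counts a previously used drug as concomitant when it ended before the first dose of the study drug.

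The cost is SAP wording and one to two extra rows per table, from variables already derived. If prior use is kept, one new derivation is needed as well. The downside is a few more unadjusted exploratory tests, with no multiplicity control under Section 9.5. Because exposure is ever/never and may begin after the reaction, a table note should say that these rows show crude association only.
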